5.2.3 Prior and Concomitant Therapy

Use of medications/supplements (including prescription or over-the-counter, vitamins and/or herbal supplements) or vaccines from the time of signing the informed consent through the Treatment Period and 30 days after study drugs are stopped, must be recorded in the electronic case report form (eCRF) at each study visit indicated in the Treatment Period ([Appendix C](#)) along with the reason for use, date(s) of administration including start and end dates, and dosage information including dose, route and frequency. The investigator should review all concomitant medications for any potential interactions.

During the Post-Treatment Period, all medications taken will be recorded until 30 days following the last dose of study drugs. After 30 days post-treatment, during the Post-Treatment Period, only antiviral therapies related to the treatment of HCV and/or

HIV and medications prescribed in association with a serious adverse event (SAE) will be recorded in EDC.

The AbbVie TA SD/TA MD should be contacted if there are any questions regarding concomitant or prior therapies.

5.2.3.1 Prior HCV Therapy

The HCV drug treatment regimen and its duration given as a part of the subject's participation in an AbbVie HCV parent study, as well as all other past HCV treatment regimens and their durations received by the subject, will be recorded in the eCRF.

5.2.3.2 Prior and Concomitant HIV-1 Therapy

If a subject is on an HIV-1 ART regimen, it must include at least one of the ARV agents defined on Inclusion Criterion 10 (Section 5.2.1).

Subjects will maintain the same dose and dosing interval of their HIV-1 ART regimen upon initiating the study drugs regimen.

Subjects must remain on the same HIV-1 ART regimen for the entire Treatment Period. Any change to an allowed HIV-1 ART regimen during the Treatment Period must be discussed with the AbbVie TA SD/TA MD prior to the change, unless the change is being made to address an immediate safety concern.

Subjects receiving any other HIV-1 ART in addition to those listed in Inclusion Criterion 10 (Section 5.2.1) would not be eligible for enrollment in the study.

5.2.3.3 Other Concomitant Therapy

Subjects should be on a stable dose of concomitant medications for at least 14 days prior to initiation of study drugs. The investigator should confirm that a concomitant medication/supplement can be safely administered with study drugs. Some medications may require dose adjustments due to the potential for drug-drug interactions.

During the Post-Treatment Period, investigators should reassess concomitant medications/supplements and subjects may resume previously prohibited medications/supplements or revert to pre-study doses, up to 14 days following discontinuation of study drugs, if applicable.

Flu shots and all essential vaccinations are allowed during Screening through the Post-Treatment Period for all subjects. Flu shots and vaccinations may affect plasma HIV-1 RNA levels.

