5.1.3 Post-Treatment Period

All subjects who received at least one dose of study drug and either complete or discontinue treatment will be monitored for an additional 24 weeks following the last dose of study drug for safety, HCV RNA and the emergence, persistence of resistance-associated viral variants, and – for HCV/HIV-1 coinfecting subjects – plasma HIV-1 RNA and HIV drug resistance.

The Post-Treatment Period will begin the day following the last dose of study drug treatment. Study visits during the Post-Treatment Period are detailed in [Appendix C](#) and Section 5.3.1.1.

Some of the Post-Treatment Period study visits and visit activities (including but not limited to vital signs, clinical laboratory tests, concomitant medication assessment) may be conducted in the home or non-hospital/clinic environment at the request of the investigator and with the agreement of the subject.

Subjects who prematurely discontinue during the Post-Treatment Period should return to the site for a Post-Treatment discontinuation visit as outlined in [Appendix C](#).

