5.2.3.4 Prohibited Therapy

Medications or supplements prohibited to be administered with ABT-493/ABT-530 are listed in [Table 9](#). For subjects in the study in countries where ABT-493/ABT-530 (glecapravir/pibrentasvir) has received marketing authorization, any medications in the local label that are contraindicated to be administered with ABT-493/ABT-530 (glecapravir/pibrentasvir) are also considered to be prohibited medications. Subjects must be able to safely discontinue any prohibited medications or supplements at least 14 days or 10 half-lives (whichever is longer) prior to the first dose of any study drug and not use these during the entire Treatment Period and for 14 days following discontinuation of study drugs. The Informed Consent Form must be signed and dated prior to discontinuing any prohibited medications or supplements for the purpose of meeting study inclusion criteria.

Table 9. Medications and Supplements Prohibited with ABT-493/ABT-530 Administration

Medication or Supplement Name
Red yeast rice (monacolin K), St. John's Wort
Carbamazepine, phenytoin, pentobarbital, phenobarbital, primidone, rifabutin, rifampin
Atorvastatin, lovastatin, simvastatin*
Astemizole, cisapride, terfenadine
Tipranavir/r, atazanavir, efavirenz, etravirine, nevirapine
Ethinyl estradiol

* Some HMG-CoA reductase inhibitors (including atorvastatin, lovastatin, or simvastatin) should not be taken with the study drug. After signing the informed consent form, subjects receiving these statins should either (a) switch to pravastatin or rosuvastatin at least 14 days or 10 half-lives (whichever is longer) prior to the first dose of study drug or (b) interrupt statin therapy throughout the treatment period beginning at least 14 days or 10 half-lives (whichever is longer) prior to the first dose of study drug and until 14 days after the last dose of study drug, based on investigator's judgment. If switching to or continuing pravastatin or rosuvastatin, it is recommended to either 1) reduce or limit the pravastatin or rosuvastatin dose in accordance with the ABT-493/ABT-530 (glecapravir/pibrentasvir) product label (if approved in the country) when taking with the study drug; or 2) reduce the pravastatin dose by 50% or limit the rosuvastatin dose to 10 mg QD when taking with the study drug, if ABT-493/ABT-530 (glecapravir/pibrentasvir) is not yet approved in the country.

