In addition, refer to the current package insert or product label for SOF and RBV for a complete list of medications prohibited to be used with those drugs, which should not be used at least 14 days prior to the first dose of any study drug, throughout the entire Treatment Period and for 14 days following discontinuation of study drugs.

Contraceptives and/or hormonal replacement therapies containing only progestins/progestogens (such as those containing norethindrone, desogestrel, or levonorgestrel) or those containing progestins/progestogens with non-ethinyl estradiol estrogens (e.g., esterified or conjugated) may be used with ABT-493/ABT-530 at the discretion of the Investigator.

Anti-HCV medications other than those specified in the protocol will not be allowed during the Treatment Period of the study.

For HCV/HIV-1 coinfecting subjects, the investigator must refer to the current package insert(s) or product label(s) of a subject's ART regimen for a complete list of medications prohibited to be used with those drugs, which should not be used at least 14 days prior to the first dose of any study drug and not use these during the entire Treatment Period and for 14 days following discontinuation of study drugs.

Use of hematopoietic growth factors is permitted during this study only with the approval of the TA SD/TA MD. Management of hematologic growth factor therapy is the responsibility of the investigator; growth factors will not be provided by AbbVie, and AbbVie will not reimburse for the expense of growth factors or their use.

Investigators should refer to the package inserts for erythropoiesis stimulating agents for additional information regarding their use.

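### Protocol Section 5.2.3.3 permits prohibited medications to be resumed during the same 14 post-treatment days in which Section 5.2.3.4 forbids them

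*Protocol*

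**What the plan says.** Protocol Section 5.2.3.3 (Other Concomitant Therapy) asks investigators to review concomitant medications once treatment has ended and states that "subjects may resume previously prohibited medications/supplements or revert to pre-study doses, up to 14 days following discontinuation of study drugs", where applicable. Section 5.1.3 fixes when that permission opens: "The Post-Treatment Period will begin the day following the last dose of study drug treatment".

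Section 5.2.3.4 (Prohibited Therapy) covers the medications in Table 9 and, where the combination is marketed, those contraindicated in the local label. Subjects must be able to stop these before the first dose and "not use these during the entire Treatment Period and for 14 days following discontinuation of study drugs". The section then applies the same interval to medications barred by the sofosbuvir and ribavirin labels, which are to be avoided "throughout the entire Treatment Period and for 14 days following discontinuation of study drugs", and again to medications barred by a co-infected subject's antiretroviral labels. The Table 9 statin footnote, in its interruption option, runs the interruption "until 14 days after the last dose of study drug, based on investigator's judgment".

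Neither section refers to the other on this point, and no order of precedence is given.

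**The concern.** The two sections sit next to each other, deal with the same medications, and use the same number of days in opposite senses. In Section 5.2.3.3 the 14 days are a time during which resumption is allowed. In Section 5.2.3.4 they are a time during which use is barred.

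The instruction is site-facing and concerns safety. Table 9 includes medications for which the Introduction reports interactions with the study drugs: exposure to ABT-493 rose up to 16-fold with ritonavir-boosted atazanavir, and exposure to both antivirals fell with efavirenz. Two sites reading different sections could manage the same patient differently. Section 7.0 does not allow intentional deviations, except to remove an immediate hazard, and requires deviations to be notified. A prohibited drug restarted on, say, post-treatment day 3 is allowed by one section and a deviation under the other.

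**Working it through.** There is no plan figure to reproduce. The check sets the provisions side by side, counting post-treatment day 1 as the day after the last dose (Section 5.1.3).

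| Provision | Medications | Effect | Post-treatment days |
|---|---|---|---|
| 5.2.3.3 | Previously prohibited medications and supplements | Resumption allowed | 1 to 14 |
| 5.2.3.4, first paragraph | Table 9 and local-label contraindications | Use barred | 1 to 14 |
| 5.2.3.4, Table 9 footnote, option (b) | Atorvastatin, lovastatin, simvastatin | Interrupted | 1 to 14 |
| 5.2.3.4, later paragraphs | Barred by sofosbuvir, ribavirin or antiretroviral labels | Use barred | 1 to 14 |
| 5.2.3.3, second limb | Medications whose dose was changed | Return to pre-study dose allowed | 1 to 14 |

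**Overlap.** For prohibited medications, the permitted days and the barred days coincide: 14 of 14.

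**Pre-study doses.** The last row has no opposing row. The bans in Section 5.2.3.4 are on use of prohibited medications. Its dose limits for pravastatin and rosuvastatin apply only while those drugs are taken together with study drug. Going back to a pre-study dose of a permitted drug after the last dose therefore contradicts nothing.

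**Can a site comply with both?** Section 5.2.3.3 grants a permission; it does not require early resumption. A site that withholds prohibited medications for all 14 days breaches neither section. The exposure is one-directional: a site that acts on Section 5.2.3.3 alone may breach Section 5.2.3.4.

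**Adverse event classification.** SAP Section 11.2.1 defines treatment-emergent status by onset date, from the first dose to 30 days after the last. Resuming a medication does not move an event into or out of that set. For a full course the window is about 84 + 30 = 114 days in Arm A and 112 + 30 = 142 days in Arm B, so the disputed days are 14/114 = 12% and 14/142 = 10% of it.

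**Recording.** Protocol Section 5.2.3 has all medications recorded until 30 days after the last dose, so early resumption would be in the database. SAP Section 7.3 does not count a drug started after the last dose as concomitant, and its post-treatment summary is confined to HCV medications. The resumption itself would therefore not appear in those two planned summaries.

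**Efficacy and sample size.** SVR12 (SAP Sections 6.2 and 10.1) is defined from post-treatment HCV RNA and does not depend on whether a Table 9 drug was resumed. The sample size (SAP Section 4.3) rests on the projected number of virologic failures in the parent studies.

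**The case against.** The best reply is that this is loose drafting of one shared interval. The amendment list in Appendix E shows both sections moving from 30 to 14 days in the same amendment, which suggests a single common window was intended. Read literally, Section 5.2.3.3 would also make day 14 the last day on which a prohibited drug could be resumed, just as the ban ends. That is an implausible rule, and no other text bars later resumption. Safeguards exist too: Section 5.2.3 tells investigators to review medications for interactions and to take questions to the sponsor's therapeutic area directors.

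Most of this stands as an account of how the wording arose. It does not remove the conflict. If the sentence is read as leaving the timing within the 14 days to the investigator, that is still discretion where Section 5.2.3.4 states a fixed bar. The safeguards help a site that notices a question, but a site reading only Section 5.2.3.3 sees a clear permission.

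The reply does defeat several stronger readings that a reader might infer:

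- That a site cannot follow both sections. It can, by withholding for 14 days.
- That the conflict includes the return to pre-study doses. The bans do not cover permitted medications.
- That the disputed days are about half of the treatment-emergent window. They are about half (14 of 30 days) only of its post-treatment tail.
- That the inconsistency changes which adverse events are treatment-emergent. Onset date alone settles that.

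**Conclusion.** The point holds as an internal contradiction limited to the resumption of prohibited medications. For those medications the permission and the bar cover the same 14 days, both are current text, and nothing says which governs. The practical result is that a site could allow use that another section forbids, and that such use cannot be consistently classed as a deviation or not.

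How often this would arise cannot be sized. It depends on how many subjects stopped a Table 9 or label-prohibited medication to enter and wished to restart it within 14 days of the last dose, and neither document gives that number. The finding assumes only that the Post-Treatment Period opens as Section 5.1.3 states and that the sentence in Section 5.2.3.3 is read as written. It is a conduct and safety-instruction point, worth correcting, with no bearing on the primary result. No view is taken on which clinical rule is right.

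**What to change.** Reconcile Section 5.2.3.3 with Section 5.2.3.4 and the Table 9 footnote, so that all three state one rule for when prohibited medications may be resumed. The sponsor's clinical team should decide which rule applies. Keep the provision on pre-study doses of permitted medications as a separate sentence, so that the correction does not merge two matters the protocol treats differently. Send sites a short clarification, and state how any resumption within the 14 days that has already occurred will be treated for deviation reporting.

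The cost is small: about a sentence of protocol text and a site communication. If it is issued as an amendment, Section 9.1 requires IEC/IRB approval and, where local regulations ask for it, regulatory approval. No analysis changes.

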5.2.3.4 Prohibited Therapy

Medications or supplements prohibited to be administered with ABT-493/ABT-530 are listed in [Table 9](#). For subjects in the study in countries where ABT-493/ABT-530 (glecapravir/pibrentasvir) has received marketing authorization, any medications in the local label that are contraindicated to be administered with ABT-493/ABT-530 (glecapravir/pibrentasvir) are also considered to be prohibited medications. Subjects must be able to safely discontinue any prohibited medications or supplements at least 14 days or 10 half-lives (whichever is longer) prior to the first dose of any study drug and not use these during the entire Treatment Period and for 14 days following discontinuation of study drugs. The Informed Consent Form must be signed and dated prior to discontinuing any prohibited medications or supplements for the purpose of meeting study inclusion criteria.

Table 9. Medications and Supplements Prohibited with ABT-493/ABT-530 Administration

Medication or Supplement Name
Red yeast rice (monacolin K), St. John's Wort
Carbamazepine, phenytoin, pentobarbital, phenobarbital, primidone, rifabutin, rifampin
Atorvastatin, lovastatin, simvastatin*
Astemizole, cisapride, terfenadine
Tipranavir/r, atazanavir, efavirenz, etravirine, nevirapine
Ethinyl estradiol

* Some HMG-CoA reductase inhibitors (including atorvastatin, lovastatin, or simvastatin) should not be taken with the study drug. After signing the informed consent form, subjects receiving these statins should either (a) switch to pravastatin or rosuvastatin at least 14 days or 10 half-lives (whichever is longer) prior to the first dose of study drug or (b) interrupt statin therapy throughout the treatment period beginning at least 14 days or 10 half-lives (whichever is longer) prior to the first dose of study drug and until 14 days after the last dose of study drug, based on investigator's judgment. If switching to or continuing pravastatin or rosuvastatin, it is recommended to either 1) reduce or limit the pravastatin or rosuvastatin dose in accordance with the ABT-493/ABT-530 (glecapravir/pibrentasvir) product label (if approved in the country) when taking with the study drug; or 2) reduce the pravastatin dose by 50% or limit the rosuvastatin dose to 10 mg QD when taking with the study drug, if ABT-493/ABT-530 (glecapravir/pibrentasvir) is not yet approved in the country.

In addition, refer to the current package insert or product label for SOF and RBV for a complete list of medications prohibited to be used with those drugs, which should not be used at least 14 days prior to the first dose of any study drug, throughout the entire Treatment Period and for 14 days following discontinuation of study drugs.

Contraceptives and/or hormonal replacement therapies containing only progestins/progestogens (such as those containing norethindrone, desogestrel, or levonorgestrel) or those containing progestins/progestogens with non-ethinyl estradiol estrogens (e.g., esterified or conjugated) may be used with ABT-493/ABT-530 at the discretion of the Investigator.

Anti-HCV medications other than those specified in the protocol will not be allowed during the Treatment Period of the study.

For HCV/HIV-1 coinfecting subjects, the investigator must refer to the current package insert(s) or product label(s) of a subject's ART regimen for a complete list of medications prohibited to be used with those drugs, which should not be used at least 14 days prior to the first dose of any study drug and not use these during the entire Treatment Period and for 14 days following discontinuation of study drugs.

Use of hematopoietic growth factors is permitted during this study only with the approval of the TA SD/TA MD. Management of hematologic growth factor therapy is the responsibility of the investigator; growth factors will not be provided by AbbVie, and AbbVie will not reimburse for the expense of growth factors or their use.

Investigators should refer to the package inserts for erythropoiesis stimulating agents for additional information regarding their use.

5.2.4 Contraception Recommendations

Female Subjects

If female, subject must be either postmenopausal defined as:

- Age \geq 55 years with no menses for 12 or more months without an alternative medical cause.
- Age $<$ 55 years with no menses for 12 or more months without an alternative medical cause AND an FSH level $>$ 40 IU/L.

OR

- Permanently surgically sterile (bilateral oophorectomy, bilateral salpingectomy or hysterectomy).

OR

Females subjects of CBP must be:

- Practicing at least one of the following methods of birth control, on Study Day 1 (or earlier) through at least 4 months after the last dose of study drug, or as directed by the local RBV label, whichever is more restrictive.
 - Progestogen-only hormonal contraception (oral, injectable, implantable) associated with inhibition of ovulation, initiated at least 1 month prior to Study Day 1.
 - Bilateral tubal occlusion/ligation or bilateral tubal occlusion via hysteroscopy (i.e., Essure), provided a hysterosalpingogram confirms success of the procedure.
 - Vasectomized partner(s), provided the vasectomized partner has received medical assessment of the surgical success and is the sole sexual partner of the CBP trial participant.
 - Intrauterine device (IUD).
 - Intrauterine hormone-releasing system (IUS).
 - True abstinence: Refraining from heterosexual intercourse when this is in line with the preferred and usual lifestyle of the subject (periodic abstinence] e.g., calendar, ovulation, symptothermal, post-ovulation methods] and withdrawal are not acceptable).

If required per local practices, male or female condom with or without spermicide OR cap, diaphragm or sponge with spermicide should be used in addition to one of the birth control methods listed above (excluding true abstinence).

Male Subjects

Male subjects who are sexually active with a female partner of CBP, even if the male subject has undergone a successful vasectomy, must agree to use condoms from Study Day 1 through at least 7 months after the last dose of study drug and his female partner(s) must use at least one of the contraceptive measures (as defined in the protocol for female

study subjects of childbearing potential). If the local RBV label for the subject has more restrictive recommendations, they must be followed instead.

Male subject must agree not to donate sperm from Study Day 1 through at least 7 months after the last dose of study drug (or as directed by the local RBV label, whichever is more restrictive).

5.3 Efficacy, Pharmacokinetic, Pharmacogenetic and Safety Assessments/Variables

5.3.1 Efficacy and Safety Measurements Assessed and Flow Chart

Study procedures described are listed in the following section of this protocol and are summarized in tabular format in [Appendix C](#).

5.3.1.1 Study Procedures

Informed Consent and RBV Information

Signed study-specific informed consent will be obtained from the subject before any study procedures are performed. All subjects will be given the RBV Medication Guide (where applicable/locally available). Male subjects will be given an additional copy of the RBV Medication Guide (where applicable/locally available) to share with their female partner(s) (where applicable/locally available). Details about how informed consent will be obtained and documented are provided in Section 9.3.

Medical History

The subject's medical history including history of tobacco, alcohol use and drug use, recorded in the AbbVie HCV parent study, will be updated at the Screening Visit with any relevant information that was not collected in the previous AbbVie study and any new medical history that occurred between the end of the previous AbbVie study and this study. In some cases, the medical history recorded in the previous AbbVie study will be electronically transferred into the eCRFs in this study and in other cases it will need to be

manually entered into the eCRFs by the site due to differences between the medical history eCRFs for the previous AbbVie study and the current study. The subject's medical history will also be updated, as needed, at the Study Day 1 Visit. This updated medical history will serve as the baseline for clinical assessment.

Physical Examination

A complete physical examination will be performed at visits specified in [Appendix C](#), or upon subject discontinuation. A symptom-directed physical examination may be performed at any other visit, when necessary.

The physical examination performed on Study Day 1 will serve as the baseline physical examination for clinical assessment. Any significant physical examination findings after the first dose will be recorded as adverse events.

Height will be measured only at Screening.

Vital Signs and Weight

Body temperature, blood pressure, waist circumference, pulse and body weight will be measured at each study visit as specified in [Appendix C](#) or upon subject discontinuation. Blood pressure and pulse rate should be measured after the subject has been sitting for at least 3 minutes and prior to blood collection. The subject will wear lightweight clothing and no shoes during weighing.

Pregnancy Testing

A serum and urine pregnancy test will be performed for all female subjects of childbearing potential at Screening and Day 1. Additional urine pregnancy tests will be performed every 4 weeks, starting at Day 1 (prior to enrollment) during the treatment period, including at the last treatment period visit and until 4 months after the last study drug dose (or as directed by local RBV label, whichever is more restrictive), as indicated in [Appendix C](#). Determination of postmenopausal status will be made during the Screening period, based on the subject's history.

Females of non-childbearing potential (either postmenopausal or permanently surgically sterile as defined above) at Screening do not require pregnancy testing.

12-Lead Electrocardiogram

A 12-lead resting ECG will be obtained at Screening. The ECG should be performed prior to blood collection.

The ECGs will be evaluated by an appropriately trained physician at the site ("local reader"). The local reader from the site will sign and date all ECG tracings and will provide his/her global interpretation as a written comment on the tracing using the following categories:

- Normal ECG
- Abnormal ECG – not clinically significant
- Abnormal ECG – clinically significant

Only the local reader's evaluation of the ECG will be collected and documented in the subject's source. The automatic machine reading (i.e., machine-generated measurements and interpretation that are automatically printed on the ECG tracing) will not be collected.

Clinical Laboratory Tests

Samples will be obtained at a minimum for the clinical laboratory tests outlined in [Table 10](#) at the visits indicated in [Appendix C](#).

Blood samples for serum chemistry tests should be collected following a minimum 8-hour fast (with the exception of the Screening Visit, which may be non-fasting). Subjects whose visits occur prior to the morning dose of study drug should be instructed to fast after midnight. Subjects whose visits occur following the morning dose of study drug should be instructed to fast after breakfast until the study visit occurs. At the Study Day 1 visit, a fasting blood sample should be collected prior to the first dose of study drug. Blood samples should still be drawn if the subject did not fast for at least 8 hours. Fasting

or non-fasting status will be recorded in the source documents and on the laboratory requisition. The baseline laboratory test results for clinical assessment for a particular test will be defined as the last measurement prior to the initial dose of study drug.

A central laboratory will be utilized to process and provide results for the clinical laboratory tests.

Instructions regarding the collection, processing, and shipping of these samples will be provided by the central laboratory chosen for this study. The certified laboratory chosen for this study is Covance. Samples will be sent to the following addresses:

Covance
[name]
[name]
(For sites in North America)

Covance
[name]
[name]
[name]
(For sites in Europe)

Covance (Asia) Pte Ltd
[name]
[name]
[name]
(For sites in Asia, Australia and New Zealand)

Table 10. Clinical Laboratory Tests

Hematology	Clinical Chemistry	Other Tests
Hematocrit	Blood Urea Nitrogen (BUN)	Anti-HIV Ab ^e
Hemoglobin	Uric Acid	FSH (all females) ^e
Red Blood Cell (RBC) count	Creatinine	Urine and Serum
White Blood Cell (WBC) count	Creatinine clearance (Cockcroft-Gault calculation)	Human Chorionic Gonadotropin (hCG) for females ^f
Neutrophils	eGFR (MDRD method)	HCV RNA
Bands, if detected	Total bilirubin ^a	HIV-1 RNA ^b
Lymphocytes	Direct and indirect bilirubin	Hemoglobin A1C ^e
Monocytes	Serum Alanine Aminotransferase (ALT)	HCV genotype and subtype ^e
Basophils	Serum Aspartate Aminotransferase (AST)	Pharmacogenetic sample (optional)
Eosinophils	Alkaline phosphatase	Alpha2-macroglobulin ^g
Platelet count (estimate not acceptable)	Gamma-glutamyl transferase (GGT)	Haptoglobin ^g
Reticulocyte count	Total protein	Apolipoprotein A1 ^g
Prothrombin Time/INR ^a	Albumin ^a	CD4, CD4% ^b
Activated partial thromboplastin time (aPTT)	Glucose	CD8, CD8% ^b
Urinalysis	Total insulin	CD4:CD8 ^b
Specific gravity	Sodium	Anti-Hepatitis A Virus IgM ^h
Ketones	Potassium	Anti-Hepatitis A Virus Total ^h
pH	Calcium	Anti-Hepatitis E Virus IgG ^h
Protein	Inorganic phosphorus	Anti-Hepatitis E Virus IgM ^h
Blood	Chloride	HEV RNA ^h
Glucose	Bicarbonate	HBsAg ^{e,h}
Urobilinogen	Magnesium	Anti-HBc IgM ^h
Bilirubin	Cholesterol	Anti-HBc Total ^h
Leukocyte esterase	Triglycerides	Anti-HBs ^h
Microscopic (reflex)	Low Density Lipoproteins (LDL) ^{b,c,d}	HBV DNA ^h
Albumin ⁱ	High Density Lipoprotein (HDL) ^{b,d}	

- a. Also a component of the Child-Pugh Assessment (along with ascites and encephalopathy).
b. Only for known HCV/HIV-1 co-infected subjects.
c. Directly measured.
d. Performed only at Day 1.
e. Performed only at Screening.
f. Females not of CBP at Screening do not require pregnancy testing as defined in Section 5.2.1 Criterion 5.

Table 10. Clinical Laboratory Tests (Continued)

- g. Component of FibroTest and collected only if needed during the Screening Period.
- h. Performed for management of transaminase elevation (Section 6.1.7.5).
- i. Collected for confirmed Creatinine Clearance < 50 mL/min, if clinically indicated as defined in Section 6.1.7.6.

For any laboratory test value outside the reference range that the investigator considers to be clinically significant:

- The investigator will repeat the test to verify the out-of-range value.
- The investigator will follow the out-of-range value to a satisfactory clinical resolution.
- A laboratory test value that requires a subject to be discontinued from the study or requires a subject to receive treatment will be recorded as an adverse event.

The management of laboratory abnormalities that may occur during the study is described in Section 6.1.7.

Hepatitis B and HIV Screen

HBsAg (hepatitis B surface antigen) and anti-HIV Ab will be performed at Screening. The investigator must discuss any local reporting requirements to local health agencies with the subject. The site will report these results per local regulations, if necessary. The HBsAg results will be reported by the central laboratory to the clinical database.

Liver Diagnostic Testing

Subjects categorized as **cirrhotic** in the AbbVie HCV parent studies will be categorized as being cirrhotic in this study.

Subjects categorized as **non-cirrhotic** in the AbbVie HCV parent studies, who do not have a qualifying liver biopsy showing absence of cirrhosis within the previous 12 months from Screening or qualifying FibroScan showing absence of cirrhosis with the previous 6 months from Screening, but who otherwise meet all of the inclusion criteria and none of

the exclusion criteria will undergo liver biopsy or non-invasive testing (FibroTest/APRI or FibroScan) prior to enrollment. Selection of liver biopsy or non-invasive testing performed should be based on local standard practice.

Subjects must be documented as non-cirrhotic or cirrhotic defined as meeting one of the following criteria:

Non-Cirrhotic

A liver biopsy within 12 months prior to or during Screening demonstrating the absence of cirrhosis, e.g., a METAVIR, Batts-Ludwig, Knodell, IASL, Scheuer, or Laennec fibrosis score of ≤ 3 , Ishak fibrosis score of ≤ 4 ; or

A FibroScan[®] score of < 12.5 kPa within ≤ 6 months of Screening or during Screening period (FibroScan[®] must be approved by the local regulatory agency to qualify for entrance criteria); or

A Screening FibroTest score of ≤ 0.48 and Aspartate Aminotransferase to Platelet Ratio Index (APRI) < 1 .

Cirrhotic

Previous histologic diagnosis of cirrhosis on liver biopsy, e.g., METAVIR, Batts-Ludwig, Knodell, IASL, Scheuer, or Laennec fibrosis score of > 3 , Ishak score of > 4 or on a liver biopsy conducted during Screening; or

A FibroScan[®] score of ≥ 12.5 kPa at any time prior to Screening or during Screening period (FibroScan[®] must be approved by the local regulatory agency); or

A Screening FibroTest result that is ≥ 0.75 and an APRI > 2 .

In the absence of a definitive diagnosis of presence or absence of cirrhosis by FibroTest/APRI using the above criteria (indeterminate FibroTest [$0.48 < \text{result} < 0.75$], or conflicting FibroTest and APRI results [e.g., FibroTest ≤ 0.48 , but APRI

≥ 1)), a liver biopsy or FibroScan[®] is required. Liver biopsy results will supersede Fibrotest/APRI or FibroScan[®] results and be considered definitive.

Subjects who are categorized as cirrhotic in this study according to the criteria above must also meet Inclusion Criteria 8 and 9.

When performed within the specified timeframes, the result of the liver biopsy supersedes the results of FibroScan and FibroTest/APRI and result of FibroScan supersedes the results of FibroTest/APRI.

Child-Pugh (Child-Turcotte-Pugh) Score and Category

The Child-Pugh (Child-Turcotte-Pugh) score uses five clinical measures of liver disease (3 laboratory parameters and 2 clinical assessments) as shown in [Table 11](#). Child-Pugh score will be determined only for subjects with compensated cirrhosis at the visits indicated in [Appendix C](#).

Table 11. Child-Pugh (Child-Turcotte-Pugh) Classification of Severity of Cirrhosis

Parameter	Points Assigned for Observed Findings		
	1	2	3
Total bilirubin, µmol/L (mg/dL)	< 34.2 (< 2)	34.2 – 51.3 (2 – 3)	> 51.3 (> 3)
Serum albumin, g/L (g/dL)	> 35 (> 3.5)	28 – 35 (2.8 – 3.5)	< 28 (< 2.8)
INR	< 1.7	1.7 – 2.3	> 2.3
Ascites*	None	Slight	Moderate to severe
Hepatic encephalopathy**	None	Grade 1 or 2 (or suppressed with medication)	Grade 3 or 4 (or refractory)

* None; Slight ascites = Ascites detectable only by ultrasound examination; Moderate ascites = Ascites manifested by moderate symmetrical distension of the abdomen; Severe ascites = Large or gross ascites with marked abdominal distension.

** Grade 0: normal consciousness, personality, neurological examination, electroencephalogram; Grade 1: restless, sleep disturbed, irritable/agitated, tremor, impaired handwriting, 5 cps waves; Grade 2: lethargic, time-disoriented, inappropriate behavior, asterixis, ataxia, slow triphasic waves; Grade 3: somnolent, stuporous, place-disoriented, hyperactive reflexes, rigidity, slower waves; Grade 4: unarousable coma, no personality/behavior, decerebrate, slow 2 to 3 cps delta activity.

Clinical Assessment of Hepatic Decompensation

A clinical assessment of hepatic encephalopathy and ascites will be performed only for subjects with compensated cirrhosis at Study Day 1 prior to dosing to confirm the subject has not progressed to hepatic decompensation since screening.

Hepatocellular Carcinoma Screening: Liver Ultrasound

HCC screening will be required as a protocol-specified study procedure only at the Screening Study Visit and at the last Post-treatment Study Visit, as indicated in [Appendix C](#), for subjects with compensated cirrhosis only. Between those visits, HCC screening should be performed according to standard of care.

At the Screening Study Visit and at the last Post-treatment Study Visit, subjects with compensated cirrhosis will be required to perform a liver ultrasound to screen for HCC,

unless the subject has a historical liver ultrasound, CT or MRI performed for HCC screening within 3 months prior to those visits, in which case the result of the historical US, CT or MRI will be used as the result for that Study Visit assessment. A positive ultrasound result suspicious of HCC will be confirmed with CT scan or MRI. Alternate methods of screening for HCC (i.e., MRI or CT) at a study visit should be discussed with the TA MD.

Enrollment and Assignment of Subject Numbers

All screening activities must be completed and reviewed prior to enrollment. Subjects who meet the eligibility criteria will proceed to enrollment via the IRT system on Day 1 (Treatment Period). Subject numbers will be unique 5-digit numbers starting with 10001. The first 3 digits will represent the investigative site and the last 2 digits will represent the subjects screened at that site. Enrolled subjects will keep their subject number throughout the study.

Study Drug Compliance for Kits

Bottles of ABT-493/ABT-530, SOF and RBV will be provided for subject dosing to the site. Each subject will have compliance documented by the site in the subject's source notes for ABT-493/ABT-530, SOF and RBV. At each drug accountability visit in [Appendix C](#), the overall number of tablets of ABT-493/ABT-530, SOF and RBV remaining in each bottle will be recorded in the source and transferred to the IRT system along with the date of reconciliation.

HCV Genotype and Subtype

Plasma samples for HCV genotype and subtype will be collected at Screening. Genotype and subtype will be assessed using the Versant[®] HCV Genotype Inno LiPA Assay, Version 2.0 or higher (LiPA; Siemens Healthcare Diagnostics, Tarrytown, NY). If the LiPA assay is unable to genotype/subtype a sample, its genotype/subtype will be determined by a Sanger sequencing assay of a region of the NS5B gene (Covance).

HCV RNA Levels

Plasma samples for HCV RNA levels will be collected as indicated in [Appendix C](#). Plasma HCV RNA levels will be determined for each sample collected by the central laboratory using the COBAS[®] AmpliPrep/COBAS[®] TaqMan HCV Quantitative Test, v2.0. For this assay, the lower limit of detection (LLOD) and the lower limit of quantification (LLOQ) are both 15 IU/mL.

HCV Resistance Testing Sample

A plasma sample for HCV resistance testing will be collected prior to dosing on Day 1 and at the study visits indicated in [Appendix C](#). Specific instructions for preparation and storage of HCV RNA and HCV resistance samples will be provided by the central laboratory, AbbVie, or its designee.

Archive Serum and Plasma Sample

